Clinical and Biochemical Evaluation of the Use of Locally Delivered Metformin as an adjunctive therapy to Non Surgical Periodontal Treatment of Periodontitis Patients

(Randomized Controlled Study)

Protocol Submitted to Department of Oral Medicine,
Periodontology and Oral Diagnosis, Faculty of Dentistry,
Ain Shams University In Partial Fulfillment of the Requirements
for Masters' Degree in Periodontology

Faculty of Dentistry

Ain Shams University

2019

Review of literature

Periodontitis is a chronic multifactorial inflammatory disease associated with dysbiotic plaque biofilms and characterized by progressive destruction of the tooth-supporting apparatus. Its primary features include the loss of periodontal tissue support, manifested through clinical attachment loss (CAL) and radiographically assessed alveolar bone loss, presence of periodontal pocketing (that are a hallmark of the disease and can eventually lead to tooth loss) and gingival bleeding (*Papapanou et al., 2018*).

The classification of periodontal diseases and conditions in 1999 included gingival diseases including (dental plaque-induced gingival diseases and non-plaque-induced gingival lesions), chronic periodontitis, aggressive periodontitis, periodontitis as a manifestation of systemic diseases, necrotizing periodontal diseases, abscess of the periodontium, periodontitis with endodontic lesions and developmental or acquired deformities (*Armitage, 1999*).

The new classification of periodontal and peri-implant diseases and conditions in 2017 classified these diseases into four main categories: First category concerned with periodontal health & gingival diseases either dental biofilm induced gingivitis and non-dental biofilm induced gingivitis. Second category concerned with periodontitis which can be classified into necrotizing periodontitis, periodontitis as a manifestation of systemic disease and periodontitis which involve the forms of the disease previously recognized as “chronic” or “aggressive”. Third category concerned with other conditions affecting the periodontium as systemic diseases, traumatic occlusion, mucogingival deformities, tooth related factors, periodontal abscesses and endodontic-periodontal diseases. Fourth category concerned with peri-implant diseases and conditions as peri-implant health, peri-implant mucositis, peri-implantitis and peri-implant soft & hard tissue deficiencies.

Periodontitis is described in four stages which depend on clinical attachment loss (CAL) ranging from Stage 1: Initial periodontitis (CAL 1-2 mm), Stage 2: Moderate periodontitis (CAL 3-4 mm), Stage 3: Severe periodontitis with potential for additional tooth loss and Stage 4: Severe periodontitis with potential for loss of dentition (CAL ≥ 5 mm). Grading focuses on assessing risk factors as smoking, systemic considerations as diabetes, and outcomes of non-surgical periodontal therapy. Grade A: Slow rate of progression (no CAL loss over 5 years), Grade B: Moderate rate of progression (CAL loss < 2 mm over 5 years) and Grade C: Rapid rate of progression (≥ 2 mm over 5 years) (*Caton et al., 2018*).

The pathogenesis of periodontal diseases is mediated by the inflammatory response to bacteria in the dental biofilm. The immune response to infection is regulated by cytokine and chemokine signals. Cytokines and chemokines (chemotactic cytokines) are the messages between cells. Cytokines are low-molecular-weight proteins involved in the initiation and further stages of inflammation, in which they regulate the amplitude and the duration of the response. The genetic regulation leading to the secretion of proinflammatory cytokines from a variety of cells is generally dependent on the activation of nuclear factor kappa-B transcription. Cytokines are produced by resident cells, such as epithelial cells and fibroblasts, and by phagocytes (neutrophils and macrophages) in the acute and early chronic phases of inflammation, and by immune cells (lymphocytes) in established and advanced lesions. After recognition and presentation of microbes to the appropriate cells, cytokines of the innate response, including tumor necrosis factor alpha, interleukin-1beta and interleukin-6, are the first to appear in the periodontal disease pathogenesis pathways. It is suggested that individuals who produce high levels of these mediators in response to the dysbiosis will experience more and severe tissue loss (**Hanada & Yoshimura, 2002**).

As an adjunctive measurement to aid proper diagnosis, evaluation of levels of various biomarkers is one possible tool. A biomarker is an indicator of a biological situation, which can help to distinguish between health and disease (**Li & Wang, 2014**). In periodontology, one of the main challenges is to identify diagnostic and prognostic biomarkers for determination of disease activity and to differentiate between health and disease (**Buduneli & Kinane, 2011**).

Sources of biomarkers for periodontal disease include saliva, serum and gingival crevicular fluid (**Ghalla, 2017**). GCF is an inflammatory exudate that can be collected at the gingival margin or within the gingival crevice which contains microorganisms, their products, and host derived substances (cytokines, enzymes, immunoglobulins, tissue degradation products, immune system cells) (**Bostanci, & Belibasakis, 2018**).

Many studies examined bone resorption biomarkers such as RANKL and OPG in GCF or in health and disease. RANKL is a TNF family member protein, in health, its principal sources are osteoblasts, in disease, it is synthesized mostly from T and B lymphocytes (**Kawai et al., 2006**). Receptor activator of nuclear factor kappa-beta (RANK) is the receptor of RANKL, located on pre-osteoclasts. RANK-RANKL interaction activates transcription factors of osteoclastogenesis (**Teitelbaum & Ross, 2003**). OPG is a soluble glycoprotein, the decoy receptor of RANKL, is synthesized from many different types of cells, Formation of RANKL-OPG complex inhibits

RANK-RANKL interaction via blocking their binding sites (**Baud'huin et al., 2013**). Elevated concentrations of RANKL in GCF of periodontitis when compared to healthy areas were demonstrated by (**Gürlek et al., 2017**).

Lowering bacterial load and inhibiting progression of inflammation are the primary treatment goals that are achieved by mechanical debridement such as scaling and root planing (SRP), a gold standard treatment for periodontitis (**Socransky & Haffajee, 2000**). However, SRP shows physical limitations in certain inaccessible areas such as deep periodontal pockets, furcations and interproximal areas of misaligned teeth, which does not allow complete reduction of anaerobic infection and recurrence (**Cobb, 2005**).

Considering these difficulties, various adjunctive treatments have been investigated to supplement Scaling and Root Planing as local delivery drugs. These include systemic and localized delivery of antibiotics (Clarithromycin gel, minocycline microspheres), chlorohexidine, bisphosphonates, statins & photodynamic therapy to reduce bacterial counts and improve clinical periodontal parameters such as probing depth reduction, gaining clinical attachment level and bone defect (BD) fill in periodontitis (**Zandbergen et al., 2013**), (**Akram et al., 2016**), (**Abduljabbar et al., 2017**).

Metformin a biguanide used in treatment of diabetes mellitus type II as an oral hypoglycemic drug, has shown stimulating effect on osteoblastic lineages leading to osteoblast differentiation and bone formation. MF increased type-I collagen production in both osteoblast-like cell lines and stimulated alkaline phosphate activity in MC3T3E1 osteoblasts (**Cortizo et al., 2005**). Since MF benefits on fracture reduction and takes positive action on osteoblasts, it appears possible that this agent may have protective effects on bone loss. Recent in vivo and in vitro studies suggest that metformin reduces receptor activator for nuclear factor-kappa B ligand (RANKL) and stimulates osteoprotegerin (OPG) expression in osteoblasts, further inhibits osteoclast differentiation and prevents bone loss in ovariectomized rats (**Mai et al., 2011**). In another study on ligature-induced periodontitis, the MF treatment of rats induced a significant reduction in alveolar bone loss compared to vehicle-treated rats (**Bak et al., 2010**).

Randomized clinical trials regarding the use of Locally delivered metformin in periodontitis, The 1% MF gel used along with Scaling and Root Planing was found to provide improvement in clinical and radiographical parameters confirmed by Studies done by (**Rao et al., 2013**) & (**Pradeep et al., 2017**) in the form of significant increase in the PD reduction, CAL gain, and improved IBD depth reduction in vertical bone defects. So In this study we will evaluate The 1% MF gel along with SRP was found to provide improvement in clinical and radiological parameters

confirmed by Studies done by (**Rao et al., 2013**) & (**Pradeep et al., 2017**) in the form of significant increase in the PD reduction, CAL gain, and improved IBD depth reduction in vertical bone defects. So In this study we will evaluate the effect of the locally delivered metformin in the form of clinical and biochemical assessment.

Aim of Study

Primary outcome :

To evaluate the clinical parameters before & after the application of locally delivered metformin as an adjunctive therapy to non surgical periodontal treatment of Stage III periodontitis.

Secondary outcome :

To measure the RANKL and OPG levels in GCF before & after application of metformin as an adjunctive therapy to non surgical periodontal treatment of Stage III periodontitis.

Subjects and Methods

Study design and Sample size calculation :

In this randomized controlled study, total sample size of 16 patients (8 patient/group) were selected for this study. The sample size was calculated to yield a 95% power in the results of this study based on the results of a previous study (Pradeep et.al., 2017) in which the authors found a significant difference in IBD depth between test and placebo groups (effect size=.2.08 mm, alpha (2 tailed)=.05). The number will be increased to 20 in each group to compensate for dropouts.

Patient Selection :

Forty patients, having periodontitis, will participate in this randomized clinical study. The subjects will be recruited consecutively from the outpatient clinic of Oral Medicine, Periodontology, oral Diagnosis and Radiology Department, Faculty of Dentistry, Ain Shams University. The purpose of the study will be explained to all patients and an informed consent will be signed before the conduction of the study. The proposal will be presented to the faculty of Dentistry Ain Shams University Research Ethics committee and have to be approved before starting the research

Inclusion Criteria will be :

1. Patients with Stage III & IV Periodontitis.
2. Age range (30 - 50) years.
3. Good compliance with the plaque control instructions following initial therapy.
4. Availability for follow up and maintenance program.

Exclusion Criteria will be :

1. Smokers
2. Systemic diseases which could influence the outcome of the therapy (According to Cornell Medical Index-Health Questionnaire).
3. Pregnant and lactating females.
4. Vulnerable groups of patients' e.g (prisoners, handicapped patients and decisionally impaired individuals).

For all patients who are suitable for the study the following clinical evaluation parameters will be measured :

- a. Plaque index (PI) (*Silness & Löe, 1964*)
- b. Gingival index (GI) (*Löe & Silness, 1963*)
- c. Probing depth (PD) (*Caton, 1980*).
- d. Clinical attachment level (CAL) (*Ramfjord, 1967*).
- e. Standardized Periapical Radiograph
 - All evaluations will be done pre operatively (base line) and 6 months post operatively.
 - Full mouth assessment will be done and then the deepest areas will be evaluated to receive the local drug.

Grouping Criteria :

The study consists of two groups, each containing 20 patients. Patients will be randomly selected using computer generated randomization (www.randomizer.org) and this will be performed by another individual other than the investigator.

Group I (20 patients) : (Treatment Group)

Supra and sub gingival scaling and root planning will be performed for patients having Stage III Periodontitis. Followed by local application of metformin gel. Oral Hygiene measures will be instructed following treatment and maintenance visits will be given to them.

Group II (20 patients) : (Control Group)

Supra and sub gingival scaling and root planning will be performed to Stage III Periodontitis patients. Followed by local application of placebo gel. Oral Hygiene measures will be instructed following treatment and maintenance visits will be given to them.

Metformin Preparation :

MF gel will be prepared, briefly all the required ingredients of the formulation will be weighed accurately. Dry gellan gum powder will be dispersed in distilled water maintained at 95°C. The dispersion will be stirred at 95°C for 20 min using a magnetic stirrer to facilitate hydration of gellan gum. The required amount of mannitol will be added to the gellan gum solution with continuous stirring and the temperature will be maintained above 80°C. Weighed amount of MF will be added with stirring. Then sucralose, citric acid, and preservatives (methylparaben, propylparaben) will be added with stirring. Finally, required amount of sodium citrate will be dissolved in 10 ml of distilled water and will be added to the mixture. The mixture will be allowed to cool to room temperature to form gel.

(Mohapatra et al., 2008)

Steps of the Research :

1. After enrollment, a detailed case history will be recorded.
2. Initial therapy by full mouth supra and subgingival scaling and root planing using ultrasonic scaler and hand instruments will be done on all patients.
3. The patients will be given instructions for self-performed plaque control measures with soft dental brush and interdental cleaning using dental floss or interdental brush.
4. Baseline sampling and the local drug delivery in both study and control groups will be performed next day of scaling to avoid contamination by blood. Samples from the gingival crevicular fluid will be collected from all selected sites using standardized sterile periopaper inserted into the deepest part of each periodontal pocket and left in situ for 30 seconds.
5. The area will be completely dried using oil free air syringe, and then the site will be isolated with cotton rolls to prevent contamination from saliva. The local drug delivery gel will be placed in the periodontal pockets using a dedicated syringe until the gel flowed out from the gingival margin.

Outcomes Assessment :

a) Clinical Assessment

Clinical Assessment will be done using William's graduated probe at baseline and six months (180 days) later.

b) Biochemical Assessment

Biochemical assessment will be done at baseline, and one month after local drug delivery. RANKL & OPG concentrations will be determined using a commercial human RANKL & OPG ELISA Kits. Measurements will be performed according to the manufacturer's instructions.

Statistical Analysis :

- All data will be collected, tabulated and statistically analyzed by appropriate statistical program.

References :

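### Neither aim states the metformin-versus-placebo contrast or a single primary endpoint, and the 95% power belongs to IBD depth, which is never defined as an outcome

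*Combined protocol and SAP*

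**What the plan says.** All references are to the combined protocol and SAP.

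- **Aim of Study.** The primary outcome is "To evaluate the clinical parameters before & after the application of locally delivered metformin as an adjunctive therapy". The secondary outcome is "To measure the RANKL and OPG levels in GCF before & after application of metformin as an adjunctive therapy". Neither mentions the control group, a summary measure or a time point.
- **Design.** The title page calls the trial a "Randomized Controlled Study". Grouping Criteria sets up two groups of 20: scaling and root planing with metformin gel, or the same with placebo gel.
- **Study design and Sample size calculation.** "The sample size was calculated to yield a 95% power in the results of this study", based on an earlier trial in which "the authors found a significant difference in IBD depth between test and placebo groups". The inputs are an effect size printed as 2.08 mm and a two-tailed alpha of 0.05, giving 8 per group. No SD is given. Then: "The number will be increased to 20 in each group to compensate for dropouts".
- **Clinical evaluation parameters.** PI, GI, PD, CAL and a "Standardized Periapical Radiograph" are listed without ranking, at baseline and 6 months. What is read from the radiograph is not stated. The deepest areas are chosen to receive the drug.
- **Outcomes Assessment.** This covers probe measurements at baseline and 6 months, and RANKL and OPG at baseline and 1 month. It contains no radiographic outcome.
- **Inclusion Criteria.** No intrabony defect is required.
- **Statistical Analysis.** One sentence, naming no test, contrast or endpoint.

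**The concern.** The question is what metformin adds to scaling. Only the randomised difference between arms isolates that, yet the aims describe change over time around metformin treatment. A change within the metformin arm would satisfy them as written.

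Because the statistics section is silent, both the contrast and the endpoint could be chosen after the data are seen. The only power figure attaches to a variable that is in neither aim and is not defined as an outcome. A reader cannot tell what power the trial has for the parameters it calls primary.

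**Working it through.** **1. Reproduce the stated sample size.** Inputs from the sample-size section: effect 2.08, two-sided alpha 0.05, power 95%, 8 per group. Assumption: 2.08 is a standardised difference d (equivalently, SD = 1 mm). For a two-sample t-test with n per arm, power = P(|T| > t(0.975, 2n−2)), where T is noncentral t with 2n−2 df and noncentrality d√(n/2).

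- n = 7: noncentrality 2.08 × √3.5 = 3.89, critical value 2.179, power 94.6%.
- n = 8: noncentrality 2.08 × √4 = 4.16, critical value 2.145, power 97.1%.

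So 8 is the smallest n reaching 95%, and the stated figure is reproduced. A one-sample (paired) test with the same d has noncentrality d√n and gives 92.7% at n = 5 and 97.9% at n = 6, so it would need 6. The calculation fits a between-arm contrast. If 2.08 is a raw difference in mm, 8 per arm is the smallest adequate n only for an SD of about 0.99 to 1.07 mm.

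**2. What 20 per arm gives for another endpoint.** The documents give no SD or expected effect for PI, GI, PD or CAL, so differences are in SDs of the analysed variable. Same formula, df = 38, critical value 2.024, noncentrality d√10, no loss to follow-up, no baseline adjustment:

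| Difference (SD) | Noncentrality | Power |
|---|---|---|
| 0.5 | 1.58 | 34% |
| 0.75 | 2.37 | 64% |
| 1.0 | 3.16 | 87% |

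Solving for d:

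| Patients per arm | 80% power | 95% power |
|---|---|---|
| 20 (no loss) | 0.91 SD | 1.17 SD |
| 16 (assumed 20% loss) | 1.02 SD | 1.32 SD |
| 8 (the calculated number) | 1.51 SD | 1.94 SD |

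The last row is a worst case: falling from 20 to 8 means 1 − 8/20 = 60% loss.

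**3. Effect of baseline adjustment.** ANCOVA multiplies the SD by √(1 − r²), with df = 37 and chance baseline imbalance ignored. The baseline-to-6-month correlation r is not in the documents. At 20 per arm:

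| Assumed r | 80% power | 95% power |
|---|---|---|
| 0.3 | 0.87 SD | 1.12 SD |
| 0.5 | 0.79 SD | 1.01 SD |
| 0.7 | 0.65 SD | 0.84 SD |

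**4. What a within-arm change contains besides metformin.** Under Steps of the Research, baseline RANKL and OPG samples are taken the day after scaling. Their change to 1 month still includes the continuing response to scaling, the effects of hygiene and maintenance, and regression to the mean at the deepest sites. For the clinical measures, the pre-operative baseline suggests a reading before scaling, in which case the change contains the whole scaling effect. The inclusion criterion "Good compliance with the plaque control instructions following initial therapy" leaves that timing open. These components are common to both arms, so the between-arm difference removes them in expectation wherever the clinical baseline falls.

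**The case against.** The strongest reply is that the comparator is not really missing. The trial is randomised, has a placebo-gel group and was sized on a test-versus-placebo difference. That stands. A reader might infer from the aims that a within-arm test is planned, but no section states one. False-positive rates worked out for such a test would describe something the plan does not contain, and they carry no weight here. What remains is that an implied contrast is not a prespecified one, and the statistics section does not supply it.

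Second, IBD depth could be the unstated reading of the radiograph, which is listed among the clinical evaluation parameters. The literature review also cites IBD depth reduction among the reported benefits of the gel. This stands too. A reader might conclude that the 95% power definitely does not apply to the primary outcome, and the documents do not support that. They support something narrower: the powered variable is never defined, and nothing links the figure to PI, GI, PD or CAL.

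Third, 20 per arm is well above the calculated 8. But the plan assigns the increase to dropouts. Without an SD or expected effect, neither adequacy nor inadequacy can be shown, so the trial should not be called underpowered.

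Finally, ANCOVA is not the only valid analysis. That is accepted in the fix.

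**Conclusion.** The concern holds, and it should be fixed before outcome data are examined. The aims name no comparator, no single primary endpoint is chosen among five listed measures, and no contrast is stated anywhere. The 95% power rests on a variable that is not defined as an outcome and that entry criteria do not guarantee patients have.

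The stated 8 per arm is not an arithmetic error if 2.08 is a standardised difference. For any of PI, GI, PD or CAL, full retention of 20 per arm gives 80% power only for a difference of at least 0.91 SD unadjusted, or 0.65 to 0.87 SD with baseline adjustment at assumed correlations of 0.7 to 0.3. These figures assume roughly normal data with one value per patient, and dropouts would make them less favourable.

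A reader might also suppose that sampling RANKL and OPG after scaling takes the scaling effect out of their before-after change. It does not: the sample is taken only one day later.

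**What to change.** Before outcome data are examined:

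1. Restate the primary objective as the metformin-minus-placebo difference at 6 months in one named endpoint.
2. Analyse one value per patient, such as the mean over treated sites, by ANCOVA on arm and baseline value, two-sided alpha 0.05, with a 95% CI. A between-arm comparison of change scores is acceptable but less precise.
3. Tie the power statement to that endpoint. Either (a) name radiographic IBD depth, define how it is read, and say how patients without an intrabony defect are handled; or (b) name another endpoint, such as CAL at treated sites, and withdraw or restate the 95% figure.
4. Make the other measures secondary. Compare RANKL and OPG between arms at 1 month with baseline adjustment, on a log scale if skewed. Report within-arm changes descriptively only.
5. State whether the clinical baseline is taken before or after scaling.

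**Cost.** Option (b) needs rewording, a standard regression and a revised power statement, with no extra visits. Option (a) also needs a defined reading of radiographs already planned and a rule for patients without a defect. In either case one parameter carries the primary claim. Under (b) the restated power may be less favourable, and the documents give no CAL effect or SD from which to judge whether 20 per arm is enough.

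### The primary outcome is an unranked set of clinical parameters with no between-group test or success rule, and the 95% power belongs to IBD depth, which is not a designated outcome

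*Combined protocol and SAP*

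**What the plan says.** - **Aim of Study, Primary outcome:** "To evaluate the clinical parameters before & after the application of locally delivered metformin", as an adjunct to non-surgical treatment. No single variable, time point or between-group contrast is named there.
- **Subjects and Methods, list of parameters:** under the words "the following clinical evaluation parameters will be measured" come PI, GI, PD, CAL and "Standardized Periapical Radiograph". They are not ranked, and no measurement on the film is defined. On timing: "All evaluations will be done pre operatively (base line) and 6 months post operatively".
- **Outcomes Assessment, Clinical Assessment:** clinical assessment is described only as probing with a graduated probe, at baseline and six months. The radiograph is not mentioned.
- **Study design and Sample size calculation:** 8 patients per group for 95% power at two-sided 0.05, from an earlier trial in which "the authors found a significant difference in IBD depth between test and placebo groups". The effect size is given as 2.08, labelled mm, with no SD. The number is then raised to 20 per group for dropouts.
- **Inclusion Criteria:** stage, age, compliance and availability. None requires an intrabony defect.
- **Statistical Analysis:** one sentence, "All data will be collected, tabulated and statistically analyzed by appropriate statistical program".

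**The concern.** A confirmatory trial needs to say in advance which result will decide the question. Here four or five parameters share primary status and nothing says how they combine. The plan as written does not prevent whichever one reaches significance from being reported as the positive primary result.

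The before-and-after wording adds a second route to an unsupported claim. Both groups receive scaling and root planing, so an improvement from baseline in the metformin group could be presented as the primary finding although it is not a comparison with placebo.

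The power statement does not close the gap. It refers to a variable that the plan does not designate as an outcome, and the documents give no effect or SD for PI, GI, PD or CAL.

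**Working it through.** **1. Which parameters are primary?** The parameter list puts the radiograph among the clinical evaluation parameters (five items). The Clinical Assessment paragraph describes probing only, which points to the four non-radiographic items. The two places are not reconciled, so both counts are carried below.

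**2. The plan's own sample size.** Inputs: effect 2.08, two-sided alpha 0.05, power 0.95, equal groups.
- Reading 2.08 as a standardised difference, the normal approximation gives n = 2 × (1.960 + 1.645)² / 2.08² = 25.99 / 4.326 = 6.01, rounded up to 7 per group. The two-sample t calculation gives 7.13, rounded up to 8, with 97.1% power at 8. The stated 8 per group is reproduced.
- Reading 2.08 literally as mm, an SD is needed and none is given. At 8 per group, 95% power requires a standardised difference of 1.941, so the SD may be at most 2.08 / 1.941 = 1.07 mm.
- At 20 evaluable patients per arm, an assumed SD of 2 mm (2.08 / 2 = 1.04 SD) gives about 89% power. An assumed SD of 3 mm (2.08 / 3 = 0.69 SD) gives about 57%.

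**3. False positives under one possible rule.** Assumptions: no true effect, each parameter tested between groups at two-sided 0.05, any one significant result counted as success. If the parameters are independent:
- Either direction, 1 − 0.95^k: 18.5% for k = 4, 22.6% for k = 5.
- Favouring metformin, 1 − 0.975^k: 9.6% for k = 4, 11.9% for k = 5, against a nominal 2.5% for a single test.

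The parameters are probably correlated, but the documents give no correlations. Simulated t-tests with 20 per arm and assumed equal correlations give, for at least one significant result in either direction:

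| Correlation | k = 4 | k = 5 |
|---|---|---|
| 0.5 | about 16% | about 18-19% |
| 0.7 | about 13% | about 15% |
| 0.9 | about 9% | about 10% |

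The chance of one favouring metformin is about half of each figure, roughly 5-9% over the table. Under the opposite rule, that all parameters must be significant, the either-direction chance is below 2% even at correlation 0.9.

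**4. What 20 completers per arm can detect on any one parameter** (two-sample t, two-sided 0.05, no baseline adjustment):
- 80% power: about 0.91 SD. The normal approximation, (1.960 + 0.842) × √(2/20) = 0.886, is slightly smaller.
- 95% power: about 1.17 SD. The normal approximation, (1.960 + 1.645) × √(2/20) = 1.140, is again slightly smaller.

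**The case against.** Several points on the other side have force.

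- *The power is attached to a named variable.* This stands. A reader might infer that nobody can tell what the 95% refers to, but the sample-size section says plainly that it is IBD depth, test against placebo. The gap is that this trial does not designate IBD depth as an outcome.
- *IBD depth is implicitly primary through the radiograph.* The film is collected, so this is possible. But no measurement on it is defined, and without an intrabony-defect criterion the quantity may not exist for every patient.
- *The sample-size arithmetic is sound.* It reproduces if 2.08 is standardised, so this point should not be read as saying that the calculation is wrong.
- *The error inflation is hypothetical.* This also stands. A reader might take 22.6% as the trial's false-positive rate. The documents do not support that: they state no success rule, the probing sentence weakens the five-parameter count, and the figure includes results against metformin.
- *The randomised placebo design already implies a between-group comparison.* It does, and so does the sample-size basis. The primary outcome and the Statistical Analysis section still do not say so.

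It is also tempting to cite the literature review, which speaks of other adjuncts used to "improve clinical periodontal parameters such as probing depth reduction, gaining clinical attachment level and bone defect (BD) fill" and later says that metformin gel "was found to provide improvement in clinical and radiographical parameters". These sentences describe earlier work and do not define this trial's outcomes. The membership question rests on the parameter list against the Clinical Assessment paragraph.

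**Conclusion.** The point holds as a fault of specification. The primary outcome is a set of four or five unranked parameters in before-and-after wording, with no between-group test, success rule or multiplicity handling. The 95% power refers to IBD depth and does not apply to PI, GI, PD or CAL. This part rests on the text alone.

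The size is illustrative. If any one significant result sufficed, a false positive in either direction would occur in about 9-23% of trials, from correlation 0.9 with four parameters to independence with five. One favouring metformin would occur in about 5-12%. Both ranges depend on the assumed rule and correlations. The plan should be changed before outcome data are seen, but the documents do not show that an inflated claim is intended.

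**What to change.** Before outcome data are seen:

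1. Name one primary variable, for example CAL or PD at treated sites, both already collected at baseline and 6 months.
2. Test the 6-month between-group difference at two-sided 0.05, with one value per patient (the unit randomised), adjusted for that variable's baseline value.
3. Make the other parameters secondary. If two primaries are kept, use Holm at a total alpha of 0.05. Its first step, at 0.025, needs about 1.01 SD for 80% power with 20 per arm, unadjusted.
4. Reword the before-and-after phrase so that the comparison with placebo is primary, and say whether the radiograph belongs to the clinical set.
5. State that the 95% power does not apply to the chosen variable, and give the detectable difference with 20 completers per arm: about 0.91 SD for 80% power and 1.17 SD for 95%, unadjusted. Baseline adjustment lowers these to the extent that baseline predicts the 6-month value.

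If IBD depth is chosen instead, define its measurement on the film and how patients without a defect are counted. The sample-size basis cannot simply be carried over: it needs an SD, clarity on whether 2.08 is mm or standardised, and the expected number of evaluable patients.

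With CAL or PD the change needs no new patients, visits or measurements. The cost is that a positive result on another index alone no longer counts as primary success, and the power statement may become less favourable.
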